5.4 Off-Study Evaluations

A symptom survey (Pediatric PROMIS Ped 25 Profile, Pain interference 8a, Physical activity 8a, Mobility 8a) and a brief interview to assess patient symptom burden will be performed at week 49 ± 3 weeks. Patients also have the option of completing vasomotor testing at week 120 ± 2 weeks.

5.5 Long-Term Follow-up Evaluations

Patients will be followed for the development of osteonecrosis as per the TOT17 protocol.

5.6 Modifications for Collaborating Sites

All sites will complete ambulatory blood pressure monitoring, Reinduction 2 MRI evaluations, serum vascular biomarkers, and symptom surveys for all patients. Vasomotor testing, echocardiography at week 17, and patient interviews will be performed only at St. Jude. Induction MRI may be performed at collaborating sites based on scanner design and sequence availability. Induction MRI may be performed at collaborating sites based on scanner design and sequence availability.

5.7 Participation of Affiliate Sites

All sites will complete ambulatory blood pressure monitoring, Reinduction 2 MRI evaluations, serum vascular biomarkers, and symptom surveys for all patients. Vasomotor testing, echocardiography at week 17, and patient interviews will be performed only at St. Jude.

6.0 EVALUATION CRITERIA

6.1 Response Criteria

All patients will be evaluated clinically and radiographically for the development of osteonecrosis. Patients with radiographic (MRI or plain film x-ray) findings of osteonecrosis will be assessed for symptoms by the treating physician or designee. CTCAE version 4 criteria will be used to categorize the severity of osteonecrosis. MRI imaging will be centrally reviewed by a radiologist blinded to treatment assignment to assess the involvement of epiphyseal surfaces (0, <30%, ≥30%) which will be determined for each effected joint.

Blood pressures for each patient will be documented in the research database as the median of each week during induction and the median of each post-induction phase.

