Brief Outline of Treatment Plan: Patients will be randomized on day 4 of induction therapy to either conventional or intensive blood pressure goals. Patients will be treated with the long-acting antihypertensive lisinopril to achieve blood pressure control as indicated by their randomized arm. Long-acting therapy will be adjusted every 3-4 days as needed to achieve targeted control based on the median of blood pressures obtained in that period. Treatment of hypertension to the target will continue until the completion of reinduction II therapy. Patients will be evaluated for osteonecrosis as indicated in their primary therapeutic protocol using MRI during reinduction II.
Study Design: Randomized unblinded trial of conventional vs. intensive hypertensive control. Evaluation of the MRIs defining the primary endpoint will be performed by a blinded radiologist.
Sample Size: We will randomize 160 evaluable patients (180 total).
Data Management: Data management and statistical analysis will be provided locally by the Comprehensive Cancer Center Hematological Malignancies Program and the Biostatistics Department at St. Jude Children’s Research Hospital.
Human Subjects: The risks to subject will be related to the toxicity of antihypertensive therapy. Side effects are anticipated to be mild and limited to reversible orthostatic/postural hypotension and transient increases in creatinine. Patients will be informed of this and other minor side effects during informed consent discussion. Adverse events will be monitored and reported and treated appropriately.

TABLE OF CONTENTS

1.0	OBJECTIVES	1
1.1	Primary Objective	1
1.2	Secondary Objectives	1
1.3	Exploratory Objectives	1
2.0	BACKGROUND AND RATIONALE	2
2.1	Background	2
2.2	Rationale	2
2.3	Background and Rationale for Ancillary and Exploratory Studies	3
3.0	RESEARCH PARTICIPANT ELIGIBILITY CRITERIA AND ENROLLMENT	4
3.1	Inclusion Criteria	4
3.2	Exclusion Criteria	4
3.3	Research Participant Recruitment and Screening	5
3.4	Enrollment on Study at St. Jude	5
3.5	Enrollment Instructions for Collaborating Sites	5
4.0	TREATMENT PLAN	6
4.1	Treatment	6
4.2	Participation of St. Jude Affiliates in the Treatment Plan	9
4.3	Treatment Modifications for Collaborating Sites	9
4.4	Supportive Care	9
4.5	Symptom Survey and Semi-structured Interviews	10
5.0	REQUIRED EVALUATIONS, TESTS, AND OBSERVATIONS	12
5.1	Pre-Study Evaluations	12
5.2	Evaluations during Therapy	12
5.3	Response Evaluations	13
5.4	Off-Study Evaluations	13

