1.2 Secondary Objectives

- 1.2.1 Evaluate the efficacy of intensive antihypertensive control compared to conventional antihypertensive control in the prevention of clinically significant (CTCAE Grade 2 or higher) and radiologically extensive osteonecrosis, overall and stratified by joints.
- 1.2.2 Compare the frequency of clinically significant and radiographically extensive osteonecrosis in patients receiving antihypertensive therapy and historical controls.
- 1.2.3 Compare blood pressures achieved in intensive and conventional arms using both pressures obtained as part of routine patient care and ambulatory blood pressure monitoring.
- 1.2.4 Compare levels of vascular dysfunction as measured physiologically, radiographically, and in blood samples in patients receiving intensive compared to standard antihypertensive therapy.

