3.1 Inclusion Criteria

- 3.1.1 Patient is being treated for newly diagnosed acute lymphoblastic leukemia or lymphoma (ALL) on the TOT17 protocol. Patients do not need to be hypertensive to enroll.
- 3.1.2 Patient is 10 years of age or older at the time of enrollment on TOT17.
- 3.1.3 Patient has completed ≤ 4 days of protocol therapy (patients are eligible on Day 4 of TOT17 therapy).

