Intensive Low End Target (mmHg)	110						
Intensive High End Target (mmHg)	120						

Patients will begin antihypertensive therapy to achieve the targeted blood pressure on Day 4 of Remission Induction on TOT17. Patients already receiving antihypertensive therapy prior to Day 4 should have their therapy adjusted according to the guidelines below.

During outpatient visits, blood pressures measured should be performed after the patient has been sitting at rest for at least 10 minutes and is not experiencing pain or anxiety.

During induction, blood pressure adjustments will be made for each patient based on the mean blood pressure over the preceding 4 days (minimum 2 measurements) unless indication for immediate change is met (listed below). Blood pressures obtained while a patient is sedated for procedures should not be included in the evaluated blood pressures when determining whether to adjust antihypertensive medications. Patients with mean blood pressures outside of the target range should have antihypertensive therapy adjusted in an attempt to reach the goal range. However, if prior changes to medication have been made within 7 days and blood pressures are both 1) closer to the target range than at the time of prior medication change and 2) within 10mmHg of the goal range following that change, further modifications can be delayed until a subsequent visit.

Immediate changes to antihypertensive therapy are indicated if:

- 1) systolic pressures are more than 15mmHg above the high end target,
- 2) patients are experiencing headache, vision changes, or neurologic symptoms attributable to hypertension,
- 3) the patient has experienced an episode of syncope,
- 4) the patient's systolic pressure is below 90, or
- 5) the patient is experiencing unacceptable toxicity from their current antihypertensive therapy.

Patients will continue antihypertensive therapy (as needed to achieve the targeted blood pressure range) during phases of therapy with scheduled glucocorticoids (i.e. Induction and Continuation, including Reinduction 1 & 2). Patients should continue antihypertensive therapy during other phases if tolerated. Caution is warranted in consolidation (due to the risk of altered renal perfusion or kidney injury) and during immunotherapy (due to the risk of cytokine release induced hypotension).

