5.2 Evaluations during Therapy

Evaluation	Timing during Induction	Timing post-Induction
Ambulatory blood pressure monitoring (ABPM)	Once for 12-30 hours on day 4-7, once for 12-30 hours on day 23-28	-
Magnetic resonance imaging of hip and knee	Once during Days 23-28#	Reinduction 2 per Total 17 protocol
Vasomotor testing (arterial elasticity, pulse wave velocity) #	Once during Days 23-28	Once between Early Intensification day 57 and Consolidation day 28, (optional) once Continuation week 120 ±2 weeks
Serum for vascular biomarkers ^{&}	Day 22 +/- 2 days	Week 17 of Continuation (Reinduction II)
Echocardiogram		Once during week 17-19 of Continuation (Reinduction II)#
Symptom survey (PROMIS: Ped 25 Profile, Pain interference 8a, Physical activity 8a, Mobility 8a)	Once on day 23-28	Week 17 of Continuation (Reinduction II) ± 2 weeks, week 49 ± 3 weeks
Semi-structured interview of treatment and symptom burden #		Week 49 ± 3 weeks (with symptom survey)

All days/ weeks refer to the date of Total 17 therapy (i.e. day 22 refers to day 22 of Total 17, not the 22nd day since HYPERION entry or randomization).

***The St. Jude IRB requires that a female patient of childbearing potential must have a negative pregnancy test as a condition of clinical research eligibility.*

SJCRH Memphis patients only

& See HYPERION Manual of Operations for collection, processing and shipping instructions.

Obtain other studies as needed for good patient care and per the TOT17 protocol.

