10.5 Secondary Objectives

Evaluate the efficacy of intensive antihypertensive control compared to conventional antihypertensive control in the prevention of clinically significant (CTCAE Grade 2 or higher) and radiologically extensive osteonecrosis, overall and stratified by joints.

A one-sided Chi-square test will be performed on a 2x2 contingency table similar to that in the primary objective, only now the columns are CTCAE Grade 2 ON (No/Yes). This analysis will also be performed for the knees and hips separately. MRI-defined extensive osteonecrosis will also be performed as described above, for knees and hip separately using Chi-square test on contingency tables.

Compare the frequency of clinically and radiographically significant osteonecrosis between patients receiving antihypertensive intervention and historical controls.

The historical control cohort consists of all patients enrolled on TOT-XV and TOT-XVI studies with age at diagnosis 10 years or older. The rate of clinically significant (CTCAE Grade 2+) ON and radiographically significant findings (number of affected joints) will be compared between the intensive BP treatment arm and the historical cohort by Chi-square tests.

Compare blood pressures achieved in intensive and conventional arms using both pressures obtained as part of routine patient care and ambulatory blood pressure monitoring.

The comparison will be done by regression modeling using mixed effect models to account for intra-patient repeated blood pressure measurements. The response variable is blood pressure, the explanatory variables include the BP control arm (intensive vs. conventional), age, sex, race and a random effect with AR(1) working covariance structure.

Compare levels of vascular dysfunction as measured physiologically, radiographically, and in blood samples in patients receiving intensive compared to standard antihypertensive therapy.

The levels of vascular dysfunction are measured by markers such as MRI, eNO synthetase, Von Willebrand Factor, TNF-alpha, D-dimer, PAI-1, E-selectin and ICAM-1; the measurements are all continuous. Each marker will be compared between the intensive BP treatment arm and the standard care arm by Wilcoxon rank-sum test.

Time frame: The analysis will begin within 6 months after the MRI assessments of the last randomized patient is completed.

Responsible investigators: [name], [name]

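### The week-1 induction blood pressure median naturally includes three pre-randomisation days, which slightly understates the routine-pressure arm contrast in objective 1.2.3

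*Combined protocol and SAP*

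**What the plan says.** Objective 1.2.3 (section 1.2) is: "Compare blood pressures achieved in intensive and conventional arms using both pressures obtained as part of routine patient care and ambulatory blood pressure monitoring".

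For the routine readings, section 6.1 fixes the stored form: "Blood pressures for each patient will be documented in the research database as the median of each week during induction". The same sentence adds one median for each post-induction phase. Section 6.1 does not say on which day week 1 starts, or whether readings taken before randomisation are entered.

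The only clock in the document is the note under the evaluation table in section 5.2: "All days/ weeks refer to the date of Total 17 therapy". That note expressly rejects counting from study entry or randomisation.

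The Protocol Summary places allocation inside the first week: "Patients will be randomized on day 4 of induction therapy to either conventional or intensive blood pressure goals". Section 4.1 starts the intervention on the same day: "Patients will begin antihypertensive therapy to achieve the targeted blood pressure on Day 4 of Remission Induction on TOT17".

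Section 10.5 analyses objective 1.2.3 with a mixed model: "The response variable is blood pressure, the explanatory variables include the BP control arm (intensive vs. conventional), age, sex, race", plus a random effect with an AR(1) working structure. Neither baseline pressure nor time is among the terms listed.

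**The concern.** Objective 1.2.3 shows whether the two pressure goals actually produced different pressures. A reader will need that to interpret the osteonecrosis result, especially a null one.

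If week 1 means TOT17 days 1-7, its median pools three days on which any arm difference is chance with four days on treatment, yet it enters the analysis as a pressure achieved on the assigned arm. The expected effect is a contrast pulled toward zero.

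The mixing happens when the value is derived. A week or arm-by-week term could isolate week 1 and leave later contrasts clean, but it could not recover the day 4-7 pressure from a median already taken over all seven days. Because days 1-3 are not stored separately, the research database would also lack a baseline pressure for adjustment, and obtaining one would mean going back to source records.

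**Working it through.** **The plan's own figure.** The documents give no SD, effect size or power for the blood pressure contrast, so there is nothing to reproduce on this point. The one stated power, 78.7% for the primary endpoint (section 10.4), reproduces as 78.66% by full enumeration of a one-sided Fisher test (0.385 v 0.20, 80 per arm). It does not depend on stored pressures.

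**Inputs from the documents**
- Randomisation and treatment start: day 4 (Protocol Summary, section 4.1).
- Week 1 = days 1-7: inferred from the section 5.2 note, not stated in 6.1.
- Target gap at age 13+: 130-135 v 110-120 mmHg (section 4.1 tables). This is 130 − 120 = 10 mmHg at the nearest edges and 132.5 − 115 = 17.5 mmHg at the midpoints.

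**Assumptions (not in the documents)**
- 4 readings a day, normal within-patient scatter with SD 6-10 mmHg, and an arm difference d of 10 or 15 mmHg fully present from day 4.
- K stored values per patient, from 4 to 12.

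**Step 1: share of days.** 3/7 = 43% of week-1 days precede randomisation. This is a share of days. The share of readings depends on measuring frequency: 3 × 1 / (3 × 1 + 4 × 6) = 11% with one reading a day before and six after, and 3 × 6 / (3 × 6 + 4 × 1) = 82% with the reverse.

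**Step 2: what the week-1 median keeps.** Simulate 28 readings per patient in each arm, with no arm difference in the first 12 and difference d in the last 16. Compare the mean week-1 medians and divide by d to get the fraction r.

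| d (mmHg) | SD 6 | SD 8 | SD 10 |
|---|---|---|---|
| 10 | 59% | 58% | 58% |
| 15 | 62% | 60% | 59% |

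When d is small relative to the SD, r falls to 4/7 = 57%. The range is therefore about 57-62%.

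If the effect is present only from day 5, r is about 38-42%. Part of that shortfall is real treatment lag, so it is not counted here.

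**Step 3: effect on the averaged contrast.** With equal weights and full separation in every period, proportional loss = (1 − r)/K.
- Smallest: (1 − 0.62)/12 = 3.2%.
- Largest: (1 − 0.58)/4 = 10.5%, or (1 − 0.57)/4 = 10.75% at the limiting r.

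**Step 4: unequal weights.** Section 10.5 names an AR(1) structure, which gives the first value in a series more weight. For K = 6 or 10 and an assumed correlation of 0.3-0.8, the first value's weight is 0.132 to 0.357. With the limiting loss of 3/7, the overall loss is 0.132 × 3/7 = 5.7% to 0.357 × 3/7 = 15.3%.

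**Step 5: slow early separation.** Suppose the true difference is 5 mmHg on days 4-7 and 10 mmHg in every later period. With SD 8, the week-1 median shows 2.89 mmHg, so 5 − 2.89 = 2.11 mmHg is lost.
- K = 4: 2.11 / (5 + 3 × 10) = 6.0%.
- K = 12: 2.11 / (5 + 11 × 10) = 1.8%.

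**The case against.** **The premise is an inference.** Section 6.1 is silent on week 1. The TOT17 note sits under a table that has no row for routine blood pressure, and patients may enter on day 4, so a site might never enter readings from days 1-3. This stands. Counting from TOT17 day 1 is the natural reading, not a stated rule. But nothing excludes those days, and the silence lets sites put different quantities in the same field.

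**There is a clean early measure.** Ambulatory monitoring on days 4-7 and 23-28 serves the same objective, excludes days 1-3, and is required at all sites (sections 5.6 and 5.7). This stands. Evidence of early separation does not rest on the week-1 routine median alone.

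**Early separation may be small.** Section 3.1 says "Patients do not need to be hypertensive to enroll", and induction adjustments look back over the preceding four days. This also stands. It reduces the absolute loss, as step 5 shows, without changing its direction.

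A reader might also draw stronger conclusions that the documents do not support:
- *That the week-1 value is 3/7 pre-randomisation pressure.* A median is not a day-weighted mean, and reading frequency is not given.
- *That the whole contrast is diluted by the loss over a few induction weeks.* Section 6.1 also stores post-induction phase medians, and the section 10.8 table runs collection through Reinduction II.
- *That patients would be wrongly dropped from the per-protocol set.* For a patient aged 13+ on the intensive arm averaging 130 mmHg before day 4 and 115 after (SD 8), the week-1 median falls in 110-120 about 31% of the time, against 96% for days 4-7. But section 6.3 does not tie its 80% criterion to weekly medians.
- *That the section 10.5 model cannot accommodate time or baseline.* Its covariate list is worded as inclusive, not closed.

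**Conclusion.** The point holds as a minor one. On the natural reading of section 6.1, one stored value per patient mixes pre- and post-randomisation readings, and no separate pre-randomisation pressure is kept. The bias in the routine-pressure contrast is toward zero, so it would not be expected to create a false separation.

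Under the stated assumptions the week-1 median keeps about 57-62% of the difference, and the contrast over 4-12 equally weighted values is about 3% to just over 10% too small. AR(1) weighting could raise that to about 15% in the settings tried, and slow early separation would lower it. Reading frequency, SD, difference and number of stored values are all assumptions.

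Only the routine-pressure part of secondary objective 1.2.3 is affected. Ambulatory readings, later weekly and phase medians, the primary MRI endpoint and its stated power are not.

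**What to change.** In section 6.1, keep TOT17 weeks but state that the week-1 induction median uses only readings from randomisation (day 4) onward. Store the median of days 1-3 as a separate pre-randomisation baseline.

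In section 10.5, state that the response for objective 1.2.3 is the post-randomisation medians only, and add the days 1-3 median as a baseline covariate.

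The cost is a sentence in each section and one extra database field. The readings already come from routine care, and no clinical rule changes. The downside is that the week-1 median rests on fewer readings. Restarting every week at day 4 would also work, but would lose alignment with the TOT17 calendar for no further gain on this point.

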6.2 Toxicity Evaluation Criteria

CTCAE version 4 (to coincide with CTCAE criteria used in TOT17) will be used to document all toxicities which occur on study.

6.3 Missed Doses

For the planned analyses, patients within targeted blood pressure ranges (or below target without the use of any antihypertensives) at least 80% of the time will be considered as part of the per-protocol analysis. All patients will be evaluated in the intention to treat analysis regardless of the blood pressure range achieved or number of doses of antihypertensives given as long as imaging to assess osteonecrosis is available.

7.0 OFF TREATMENT AND OFF STUDY CRITERIA

7.1 Off-Study Criteria

- Death
- Lost to follow-up
- Request of the patient/parent/LAR
- Completion/discontinuation of Total 17 therapy
- Discretion of the Study PI, such as the following
- The researcher decides that continuing in the study would be harmful, such as:
 - A treatment is needed that is not allowed on this study
 - The participant misses so many appointments that the data cannot be used in the study
 - The participant's condition gets worse
 - New information is learned that a better treatment is available, or that the study is not in the participant's best interest
 - Study evaluations are complete

7.2 Off-Therapy Criteria

- Completion of prescribed therapy duration (completion of week 19 dexamethasone).
- Discontinuation of TOT17 therapy
- Treatment with high-risk arm therapy (i.e. chimeric antigen receptor T-cell therapy, Reintensification, or transplant)
- Development of unacceptable toxicity during treatment
- Refusal of therapy
- A research participant may also be taken off treatment or off of the study at the discretion of the study PI if persistent non-adherence with protocol directed therapy is documented.

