5.3 Response Evaluations

Osteonecrosis will be graded according to CTCAE v4 (to coincide with CTCAE version used in TOT17). Patients will receive MRI screening during Reinduction II as prescribed in the TOT17 protocol. Pain will be ascribed to osteonecrosis or an alternative cause by the treating physician based on clinical history, radiographic findings, and response to therapeutic interventions. MRIs obtained at other times due to clinical concerns/symptoms will be recorded in the research database. MRIs will be evaluated by a pediatric radiologist blinded to the hypertension randomization.

Induction MRIs will only be performed in patients able to complete the study without sedation.

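### Sections 7.1 and 7.2 let the PI of an open-label trial end study participation, not only treatment, and Section 10.1 then replaces the patient, against the promised intention-to-treat analysis

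*Combined protocol and SAP*

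**What the plan says.** - **Off study for non-adherence.** Section 7.2 is headed as off-therapy criteria, but its last item says a participant may be "taken off treatment or off of the study at the discretion of the study PI if persistent non-adherence with protocol directed therapy is documented".
- **Off study by discretion.** Section 7.1 lists "Discretion of the Study PI, such as the following". Beneath it, as examples of continuation being harmful, come "The participant misses so many appointments that the data cannot be used in the study" and "The participant's condition gets worse".
- **Blinding.** The Protocol Summary describes a "Randomized unblinded trial of conventional vs. intensive hypertensive control". Only the radiologist reading the MRIs is described as blinded (Protocol Summary, Sections 5.3 and 6.1).
- **Consequence of exit.** Section 10.1 makes patients who drop out for a 7.1 or 7.2 reason, before osteonecrosis is observed or before the Reinduction II MRI, inevaluable for the primary endpoint and replaces them.
- **Analysis promise.** Section 6.3 includes all patients in the intention-to-treat analysis "regardless of the blood pressure range achieved or number of doses of antihypertensives given", provided imaging is available. Section 10.4 counts every randomized patient with appropriate imaging as evaluable.
- **Source of the endpoint.** Section 5.3: "Patients will receive MRI screening during Reinduction II as prescribed in the TOT17 protocol".
- **Data after removal.** Section 9.1 states adverse event collection for 4 weeks after removal from treatment. Section 5.4 lists a symptom survey, an interview and optional vasomotor testing. Neither mentions retrieving the MRI of a patient who is off study.

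**The concern.** Stopping the intervention and stopping follow-up are different decisions, and the plan merges them. A patient who does not take the antihypertensive can leave the study altogether and be replaced, which is the patient an intention-to-treat analysis is meant to keep. The decision sits with the PI of an open-label trial. No section states the PI's own blinding status, so knowledge of the arm is an inference from the design.

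The reasons may not be neutral between arms. Only a patient who is prescribed a drug can fail to take it, and the lower targets in Tables 1b and 2b make it likely that more intensive-arm patients are prescribed one. Section 4.1 has the research team verify adherence at least weekly, so the trigger is in routine use. Blinded reading protects how an MRI is scored, not which patients have one scored.

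At stake is whether the one-sided primary test still compares the groups as randomized. The loss is largely avoidable: a patient who stops antihypertensives but stays on TOT17 is still due the endpoint MRI. Section 6.3 also already provides a per-protocol set, defined by time in the target range, so removal is not needed for that purpose.

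**Working it through.** **1. The plan's own figure.** Inputs from Section 10.4: 80 per arm, 38.5% v 20% with at least one affected joint, one-sided 5%. Enumerating all outcomes of two binomials with the one-sided Fisher exact test gives power 78.66%, against 78.7% stated. With 38.5% in both arms, the same test rejects in 3.4% of trials. That is the baseline type I error.

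**2. Removal model.** No true effect; a share g of drug-takers is removed as non-adherent and replaced, leaving 80 per arm.
- Share of the intensive arm on drug: 1 − 0.146 = 0.854 (Section 10.4: 14.6% within target untreated).
- Share of the standard arm on drug: 94/235 = 0.40 (Section 2.1: developed hypertension).
- Both shares are stand-ins, because the documents do not give drug need under this trial's targets.
- g = 10% or 20% (assumption). Fraction removed f = 0.854g, or 8.5–17.1%, in the intensive arm; f = 0.40g, or 4–8%, in the standard arm.
- b = osteonecrosis risk of removed patients (assumption, varied both ways). The documents give no risk by adherence. The closest figure is the above-target group in Section 10.4: 50/120 = 41.7%.
- Observed arm rate = (0.385 − f·b)/(1 − f).

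Example, g = 20% and b = 60%: intensive (0.385 − 0.171 × 0.6)/(1 − 0.171) = 0.341; standard (0.385 − 0.08 × 0.6)/(1 − 0.08) = 0.366; type I error 7.2%.

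| Risk of removed patients | g = 10% | g = 20% |
|---|---|---|
| 20% | 2.6% | 1.7% |
| 30% | 3.0% | 2.5% |
| 38.5% (unrelated to outcome) | 3.4% | 3.4% |
| 41.7% | 3.6% | 3.8% |
| 50% | 4.1% | 5.1% |
| 60% | 4.8% | 7.2% |

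**3. Equal removal.** If the intensive-arm fraction (8.5–17.1%) is removed from both arms at 50–60% risk, type I error is 3.5–3.6%. The difference between arms drives the result.

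**4. Against the drop-out allowance.** At g = 20% the average removal is (17.1 + 8)/2 = 12.5%, so non-adherence alone would use up the 12% in Section 10.1. At g = 10% it is (8.5 + 4)/2 = 6.3%, and every result in that column stays below 5%.

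**The case against.** **Direction.** A reader might infer that removal biases the test towards benefit. The documents do not support that as a fact. It needs removed patients to carry above-average risk, and under the null used here missed antihypertensives cannot cause such risk; it would have to come through prognosis. With lower-risk patients removed, the test becomes more conservative. This objection stands.

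**Arm contrast.** The 85% and 40% come from different cohorts and different definitions: within target untreated among TOTXVI patients, and hypertension developing on Total XV and XVI. This stands. The contrast illustrates the mechanism and does not forecast it.

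**Worsening.** A reader might take the worsening item in Section 7.1 to cover joint symptoms, so that patients with osteonecrosis are removed. If 1 to 4 such patients left the intensive arm only and were replaced, its rate would be (30.8 − k + 0.385k)/80 and type I error 4.3–7.9%. But the item is an example of continuation being harmful, and joint symptoms are not mentioned. Section 5.3 records symptom-triggered MRIs, Section 9.1 records Grade 2+ osteonecrosis, and Section 10.1 refers to drop-out before osteonecrosis is observed. I do not rely on this scenario.

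**Already covered.** Sections 6.3 and 10.4 keep everyone with imaging. That helps only if an off-study patient's MRI is retrieved and read. The documents are silent on this; they do not say reading stops. Sections 6.3, 10.1 and 10.4 agree only if every 7.1 or 7.2 exit lacks an MRI, which need not be so for patients still on TOT17.

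**Lost data.** Patients who miss many visits may also miss the TOT17 MRI, so not every endpoint can be recovered. This stands.

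**Conclusion.** The concern holds as a conflict between sections with a credible route to selection. Sections 7.1 and 7.2 allow study removal for reasons that may depend on arm or prognosis, and Section 10.1 replaces those patients, whereas Sections 6.3 and 10.4 promise analysis as randomized. It is worth correcting before patients are removed on these grounds.

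The size is not known. Against a 3.4% baseline, the illustrated type I error runs from 1.7% to 7.2%. It exceeds the nominal 5% only at 20% removal of drug-takers with an assumed risk of 50–60%. At the plan's own above-target risk it is 3.6–3.8%, and it stays at about 3.4–3.6% if removal is unrelated to outcome, or equal in both arms at 50–60% risk. These figures rest on the assumed removal shares, the borrowed 85% v 40% drug need and the assumed risk of removed patients. The stated power is not in dispute.

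**What to change.** 1. **Section 7.2:** delete the option of removal from the study in the non-adherence item, leaving removal from treatment.
2. **Section 7.1:** state that a patient stopped for PI discretion, non-adherence, missed visits or worsening, who remains on TOT17 and has not withdrawn consent, leaves the blood pressure intervention only. The TOT17 Reinduction II MRI is still collected and read blinded, and Grade 2+ osteonecrosis is still recorded.
3. **Section 10.1:** state that patients off the intervention who have a Reinduction II MRI are analysed as randomized, and are neither labelled inevaluable nor replaced. Without this, steps 1 and 2 fail, because leaving the intervention is itself a 7.2 reason.
4. **Reporting:** tabulate off-study and off-intervention reasons by arm.

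Rules for stopping treatment are unchanged, and no procedure is added.

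**Cost:** record abstraction for a few off-treatment patients, and possible dilution of the observed effect. As an illustration, suppose the MRI were available for all 180 randomized (90 per arm). Exact power would be 82.9% at the planned rates. If 5 of 90 intensive-arm patients carried the control rate, the arm rate would be (85 × 0.20 + 5 × 0.385)/90 = 0.210 and power 78.2%. With 10 of 90 it would be (80 × 0.20 + 10 × 0.385)/90 = 0.221 and power 72.9%. That dilution belongs to the intention-to-treat effect the plan says it will estimate.
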